**Open Label Extension:**

- The incidence and severity of TEAEs;
- Vital signs and physical examinations;
- Laboratory values;
- 12-lead ECGs; and
- C-SSRS.

**NOTE:** Effective 16 February 2021, the OLE portion of the study was terminated by the Sponsor.

**Statistical Considerations**

The study is designed as an adaptive trial and will allow for stopping early for efficacy, futility and potential adjustment in sample size based on the results of a planned interim analysis. Approximately 573 subjects are planned to be randomized 1:1:1 per treatment group (191 per treatment group) assuming approximately 10% will drop out prior to 48 weeks. This sample size would provide approximately 90% power to detect a 2.5-point difference between active treatment group and placebo with respect to change from baseline ADAS-Cog 11 score at Week 48, assuming a standard deviation of 7.1 at a two-sided significance level of 0.05 using a two-sided test. The ADCS-ADL was added as a co-primary outcome, with assumptions of a 3.9-point difference between the active treatment group compared to placebo with respect to change from baseline on ADCS-ADL, assuming a standard deviation of 10.5, providing approximately 95% power on this outcome measure, with approximately 90% power for the overall co-primary outcomes, depending on their correlation.

An unblinded interim analysis will be conducted by a firewalled independent statistician (all clinical trial personnel will remain blinded) when approximately 100 subjects per arm have completed the Week 24 visit. Overwhelming efficacy, futility and sample size adjustment will be evaluated. The Lan-DeMets spending function will be used to determine the test boundaries. If the interim analysis is conducted when approximately 300 subjects have completed the Week 24 visit, then a significance level of 0.005 will be used for the interim analysis and a

significance level of approximately 0.0456 will be used for the final analysis.  
Further details are provided in the statistical analysis plan (SAP).

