### **11.2 Determination of Sample Size**

The study will have an adaptive design that allows for potential adjustment in sample size and evaluation of efficacy based on the results of a planned interim analysis. An unblinded interim analysis will be conducted by a firewalled independent statistician (all clinical trial personnel will remain blinded) when approximately 100 subjects per arm have completed the Week 24 visit. Approximately 573 subjects are planned to be randomized 1:1:1 per treatment group (191 per treatment group) assuming approximately 10% will drop out prior to 48 weeks. Due to the planned interim analysis, adjustments will be made to the alpha level used in the final analysis to control for overall Type I error. The final criterion for efficacy to be used at the interim and final analysis depends on when the interim analysis occurs. The Lan-DeMets method modified according to [Chen et al. \(2004\)](#) to account for correlation between endpoints used at the interim and final analyses will be used to calculate the level of significance for each analysis. As originally planned, with 573 subjects randomized, an expected 10% discontinuation rate, and a single primary outcome, a total of 172 subjects per treatment group would provide approximately 90% power to detect a 2.5-point difference between the active treatment group compared to placebo with respect to change from baseline on the ADAS-Cog 11, assuming a standard deviation of 7.1, respectively at a significance level (alpha) of 0.05 using a two-sided test. The ADCS-ADL was added as a co-primary outcome, with assumptions of a 3.9-point difference between the active treatment group compared to placebo with respect to change from baseline on ADCS-ADL, assuming a standard deviation of 10.5, providing approximately 95% power on this outcome

measure, with approximately 90% power for the overall co-primary outcomes, depending on their correlation.

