#### **11.3.2 Efficacy Analysis**

##### **11.3.2.1 Primary Efficacy Analysis**

The co-primary endpoints are the mean change from baseline in ADAS-Cog 11 at the end of the study (average of Weeks 40 and 48), and the mean change from baseline in the Alzheimer's Disease Cooperative Study – Activities of Daily Living (ADCS-ADL) at the end of the study (average of Weeks 40 and 48).

Each of the coprimary endpoints will be analyzed using a mixed-effects model for repeated measures (MMRM) with SAS PROC MIXED to compare change from baseline for COR388 HCl vs placebo. The MMRM model will include treatment group, study visit, site/country, treatment group by study visit interaction as fixed effects, and baseline MMSE (average of the last two non-missing assessments

collected prior to or at the day of first dose of the IP), ApoE4 status, and acetylcholinesterase inhibitor and/or memantine usage at baseline as factors with baseline score as a covariate using the ITT population. The analysis will be based on unstructured covariance matrix to model the within-subject errors. A Kenward-Roger approximation will be used for the denominator degrees of freedom.

Summary statistics (n, mean, standard deviation, minimum, median, and maximum) will be presented for the observed values for each of the coprimary endpoints at each time point for the ITT population, including weeks 40 and 48 separate as well as averaged. Summary statistics will also be presented for the change from baseline values to each postbaseline time point as listed above.

The Type I error for the interim and final analysis will be adjusted using the Lan-DeMets spending function. Detailed of the adjustment is presented in [Section 11.3.2.3](#) and in the [SAP](#).

Treatment comparisons of 40 mg and 80 mg COR388 HCl to placebo will be adjusted using Benjamini-Hochberg multiplicity adjustment procedure ([Benjamini and Hochberg, 1995](#) and [Benjamini and Yekutieli, 2001](#)). Both treatment comparisons, 40 mg (low dose) and 80 mg COR388 HCl (high dose) to placebo are considered of equal interest.

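### The stated overall co-primary power of about 90% is an upper limit: at 172 evaluable subjects per arm the protocol's own inputs give about 84–88%

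*Protocol*

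**What the plan says.** The synopsis (Statistical Considerations) and section 11.2 plan 573 randomised subjects, 191 per arm, with about 10% dropout before Week 48. Section 11.2 turns this into an evaluable number, for the plan as it stood with a single primary outcome: "a total of 172 subjects per treatment group would provide approximately 90% power" for a 2.5-point ADAS-Cog 11 difference with SD 7.1 at two-sided alpha 0.05. The synopsis places that difference in time: "with respect to change from baseline ADAS-Cog 11 score at Week 48".

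ADCS-ADL was added as a co-primary endpoint with a 3.9-point difference and SD 10.5, "providing approximately 95% power on this outcome measure, with approximately 90% power for the overall co-primary outcomes, depending on their correlation". Section 11.2 repeats the statement. Neither place gives a correlation, or a separate n for the ADCS-ADL and overall figures.

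Three other statements bear on the number:
- After the interim analysis, a "significance level of approximately 0.0456 will be used for the final analysis".
- Section 11.3.2.1 defines the endpoint as the "mean change from baseline in ADAS-Cog 11 at the end of the study (average of Weeks 40 and 48"), and ADCS-ADL likewise, analysed by a covariate-adjusted MMRM.
- On the two doses, the same section says: "Treatment comparisons of 40 mg and 80 mg COR388 HCl to placebo will be adjusted using Benjamini-Hochberg multiplicity adjustment procedure".

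That both endpoints must be won follows from the term co-primary. It is consistent with sections 11.3.2.2 and 11.3.2.3, which open the secondary tests only when both are significant, and with section 11.3.5, which requires both interim endpoints for an efficacy stop.

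**The concern.** The chance of winning on two endpoints is at most the chance of winning on the weaker one. If ADAS-Cog 11 has about 90% power, about 90% for both is the best case, reached only when the second endpoint costs almost nothing. The reference to the correlation reads as if 90% were a central value that could move either way. On the stated inputs it can essentially only move down.

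This is the headline power for success on the co-primary pair, and it is printed twice. It suggests that adding a second required endpoint to an unchanged sample of 573 cost no power. A reader who later weighs a negative result, or an interim sample-size decision, would start from too favourable a figure and could not tell which n, alpha, correlation or visit it rests on.

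**Working it through.** **Inputs** (synopsis and section 11.2): ADAS-Cog 11 difference 2.5, SD 7.1; ADCS-ADL difference 3.9, SD 10.5; 191 randomised per arm, 191 × 0.9 = 171.9, so 172 evaluable; alpha 0.05 two-sided, or 0.0456 at the final analysis. The endpoint correlation ρ is not given, so 0 to 0.8 is assumed.

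**Formulas.** Power on one endpoint = Φ(m), with m = δ / (SD·√(2/n)) − z(1−α/2). Power on both = Φ₂(m₁, m₂; ρ), the bivariate normal probability that both tests pass.

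**Step 1: the plan's own single-endpoint figures, n = 172, alpha 0.05.** √(2/172) = 0.1078.
- ADAS-Cog 11: 2.5 / (7.1 × 0.1078) = 3.265; 3.265 − 1.960 = 1.305; power 90.4%. The stated 90% reproduces.
- ADCS-ADL: 3.9 / (10.5 × 0.1078) = 3.445; 3.445 − 1.960 = 1.485; power 93.1%. This is a borderline miss against the stated 95%.

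The noncentral t gives 90.2% and 93.0%.

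**Step 2: both endpoints, one dose against placebo.**

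| n per arm, alpha | ADAS-Cog 11 | ADCS-ADL | both, ρ = 0 | ρ = 0.5 | ρ = 0.8 | limit as ρ → 1 |
|---|---|---|---|---|---|---|
| 172, 0.05 | 90.4% | 93.1% | 84.2% | 85.9% | 87.9% | 90.4% |
| 172, 0.0456 | 89.7% | 92.6% | 83.1% | 85.0% | 87.0% | 89.7% |
| 191, 0.05 | 93.1% | 95.3% | 88.7% | 89.8% | 91.2% | 93.1% |

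At 172 per arm and alpha 0.05, joint power is 88.9% at ρ = 0.9 and reaches 90.0% only at about ρ = 0.97.

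**Step 3: the same test without choosing n, SD or alpha.** Taking the printed 90% and 95% at face value, joint power is 85.5%, 86.9% and 88.5% at ρ = 0, 0.5 and 0.8, with a limit of 90%.

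**Step 4: which basis gives the printed numbers?** The 95% and the joint 90% fit the 191 row, which has no dropout. The ADAS-Cog 11 90% fits the 172 rows. No row of the table gives all three for ρ between 0 and 0.8.

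**The case against.** The strongest reply is that 172 belongs to the single-outcome calculation and the added ADCS-ADL sentence names no n. At 191 per arm the added figures come out. But 191 ignores the 10% dropout assumed in the same paragraph, and it would make ADAS-Cog 11 93%, not 90%. The three figures would still not share a basis.

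Second, the planned analysis may be more efficient than a two-sample comparison at one visit. Averaging two visits that correlate at 0.8 multiplies the SD by √((1 + 0.8)/2) = 0.949 and gives joint power of 88.7–91.2% at n = 172, alpha 0.05 and ρ = 0–0.8. Covariates that explain 10% of the variance have the same effect, since √0.9 = 0.949. Partial MMRM data equivalent to 182 per arm would give 86.7–89.7%. These inputs are assumptions. The power text invokes none of them, and the synopsis names Week 48. What stands is that 90% may have been meant on such a basis, which should then be stated.

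Third, the sentence is hedged and says approximately. That stands too: the figure is optimistic rather than impossible, and the 6-point gap needs zero correlation.

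A reader might also infer that the Benjamini-Hochberg adjustment makes the gap much larger. The documents do not support that. The printed sentence compares one active group with placebo, and the power text does not say how the two-dose rule combines with the co-primary requirement. If the rule is applied to each dose's larger p-value at 0.0456 (an assumption), power is about 74–80% when only one dose works, but 89–92% for at least one dose when both work. The direction depends on a definition of success that the power text does not give.

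**Conclusion.** The point holds. At 172 evaluable per arm, with the stated differences and SDs, the overall co-primary power for one dose against placebo is about 84–88% at alpha 0.05 and 83–87% at 0.0456, for a correlation of 0–0.8. At alpha 0.05 the printed 90% is about 2–4 points too high at correlations of 0.5–0.8 and up to 6 points at zero. The arithmetic is firm. The correlation range is assumed, and the calculation is a single-visit comparison that models neither the interim efficacy stop nor a sample-size increase.

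That dropout was left out of the two added figures is a plausible inference from the match with 191 per arm, but the text does not say so. Nor does the point show that 573 subjects is the wrong number: the documents tie that number to the original single outcome and allow an interim sample-size adjustment. What is wrong is the stated power and its unlabelled basis.

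**What to change.** In the synopsis (Statistical Considerations) and section 11.2, restate all three power figures on one labelled basis: evaluable n per arm, alpha, assumed endpoint correlation, visit, and a single dose-placebo comparison before multiplicity adjustment. With 172 per arm and the stated differences and SDs, for a correlation of 0–0.8, the figures are:
- alpha 0.05: ADAS-Cog 11 about 90%, ADCS-ADL about 93%, both about 84–88%;
- alpha 0.0456: about 90%, about 93%, both about 83–87%.

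If 90% was meant on another basis (averaged Weeks 40 and 48, covariate-adjusted or partial MMRM data, or success on at least one dose), state that basis and its assumptions instead. Add a note that the figures are before the two-dose Benjamini-Hochberg adjustment.

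The cost is wording in two places and a slightly less favourable stated power. Patients, tests and alpha stay as they are.

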**Table 1. Schedule of Evaluations – Double-blind study**

Study Period	Screening	Treatment Period																Safety Follow-up (if not participating in open label extension portion  )		
		2	3	3a	4	4a	4b	5	5a	6	6a	7	7a	8	9	10/ET 	Phone Call	11		
Visit number	1	2	3	3a	4	4a	4b	5	5a	6	6a	7	7a	8	9	10/ET 	49	51	54	
Week	-6 to -1	0	2	4	6	8	10	12	15	18	21	24	28	32	40	48	49	51	54	
Day	-42 to -1	0 - 7	14 ± 2	28 ± 3	42 ± 3	56 ± 3	70 ± 3	84 ± 3	105 ± 3	126 ± 3	147 ± 3	168 ± 3	196 ± 3	224 ± 3	280 ± 8	336 ± 8	343 ± 2	357 ± 2	378 ± 8	
Evaluations																				
Informed Consent	X															X 				
Inclusion/Exclusion Criteria	X	X														X 				
Medical History and confirmation of cognitive decline in the last 12 months	X																			
Full Physical Examination, Height, and BMI Calculation	X																			
MRI (or CT) of the Brain	X															X 				
Modified Hachinski	X																			
MMSE 	X	X						X				X			X	X			X	
Randomization		X																		
ADAS-Cog 11	X	X						X				X			X	X			X	
ADCS-ADL		X						X				X			X	X			X	
CDR-SB	X	X						X				X			X	X			X	
NPI		X										X				X				
Winterlight Speech Assessment (only in English speaking (primary language) subjects and only in the US and UK)	X	X						X				X				X				
Dispense Study Drug		X	X		X			X				X			X	X 				
Concomitant Medications	X	X	X		X			X		X		X		X	X	X	X	X	X	
Oral Examination and collection of oral biomarker samples (only at selected sites) 	X											X 				X 				
Saliva Collection	X	X										X				X			X	
Symptom-Based Physical Examination		X	X		X			X		X		X		X	X	X			X	
Weight	X															X				
Vital Signs	X	X	X		X			X		X		X		X	X	X			X	
Columbia-Suicide Severity Rating Scale	X	X	X		X			X		X		X		X	X	X			X	

Footnotes appear on following page.

**Table 1. Schedule of Evaluations – Double-blind study (Continued)**

Study Period	Screening	Treatment Period																Safety Follow-up (if not participating in open label extension portion  )		
		2	3	3a	4	4a	4b	5	5a	6	6a	7	7a	8	9	10/ET 	Phone Call	11		
Visit number	1	2	3	3a	4	4a	4b	5	5a	6	6a	7	7a	8	9	10/ET 	Phone Call	11		
Week	-6 to -1	0	2	4	6	8	10	12	15	18	21	24	28	32	40	48	49	51	54	
Day	-42 to -1	0 - 7	14	28	42	56	70	84	105	126	147	168	196	224	280	336	343	357	378	
			± 2	± 3	± 3	± 3	± 3	± 3	± 3	± 3	± 3	± 3	± 3	± 3	± 8	± 8	± 2	± 2	± 8	
Evaluations																				
Safety Laboratory Tests 	X	X	X		X			X		X		X		X	X	X			X	
Liver Safety Monitoring 				X		X	X		X		X		X							
Lumbar Puncture (LP) 		X														X				
Adverse Events		X	X		X			X		X		X		X	X	X	X	X	X	
Blood Collection for PK 		X	X									X			X	X				
12-Lead ECG	X	X 	X 		X			X				X 			X 	X 			X	
ApoE Genotyping	X																			
Urine Collection Pregnancy  Test	X															X				
Blood Collection for FSH 	X																			
Serum and whole blood (PBMCs) for biomarkers		X										X				X				
Blood Collection for Serology (HCV-Ab, HBsAg, HIV 1 and 2)	X																			
Blood Collection for Vit. B12, Thyroid function tests and Syphilis	X																			
Urine Collection for Drug Screen	X	X																		

 
1. Visit 10/ET MRI will be done only in subjects who had a screening MRI performed and may be done up to 8 days prior to Visit 10/ET. CT scans of the brain can be used instead of MRIs, only in subjects who have an absolute contraindication for MRI.
 
2. Administer the first MMSE as early in the screening period as possible. MMSE score should be <math>\geq 12</math> and <math>\leq 24</math> at both screening and Visit 2, and a <math>\leq 3</math>-point difference between visits, for inclusion in the study.
 
3. Oral biomarker samples include subgingival plaque and buccal cell swabs (only at selected sites).
 
4. Subjects will have follow-up oral examinations at 24 and 48 weeks.
 
5. Visit 10/ET oral examinations may be completed up to 8 days prior to Visit 10 (or ET) when applicable.
 
6. Baseline (V2) LP must be done after the baseline MMSE score has been verified and subject's eligibility has been confirmed, and prior to the first dose of study drug. To allow flexibility of scheduling the LP procedure, the MMSE and then the LP may be performed up to 7 days prior to baseline V2. Likewise, the LP at Visit10/ET may be performed up to 7 days prior to the other visit procedures, even if the LP is outside the visit window. The LP procedures must be
 
																				

- performed as per SOC and site specific SOPs, if applicable (including imaging before and/or during the LP, if required).
7. A pre-dose trough sample will be drawn at all visits 2, 3, and 7 immediately prior to the AM dose, and the subject will then take their dose of study drug on-site. The exact times of AM dosing and PK sample collections at the site will be documented. A single post-dose sample will be drawn from each subject while on-site at the clinic per the following schedule: V2 30 minutes - 4 hours; V3 60 minutes ± 30 minutes; V7 2 hours ± 30 minutes; V9 3 hours ± 30 minutes; and V10/ET 4 hours ± 30 minutes.
  8. At visits when the subject takes their dose of study drug on-site, ECGs should be measured approximately 1-1.5 hours after dosing.
  9. At Visit 3 and Visit 7, ECGs will also be performed at trough (prior to dosing).
  10. A urine pregnancy test will be conducted only in women of child bearing potential at screening and End of Treatment or Early Termination Visit 10, and at other visits only if indicated. If the urine pregnancy test is positive, a serum pregnancy test will be performed to confirm pregnancy.
  11. Only for peri-menopausal (irregular menstrual periods) or post-menopausal (no menstrual period for >12 months) female subjects.
  12. Subjects who want to participate in the open label extension portion of the study will complete the Week 48 visit and then continue with the Schedule of Evaluations in Table 2. **NOTE:** Effective 16 February 2021, the OLE portion of the study was terminated by the Sponsor.
  13. Informed consent will be obtained for subjects who agree to participate in the open label extension portion of the study.
  14. Inclusion/exclusion will be evaluated to determine eligibility for subjects who want to participate in the open label extension portion of the study. Laboratory testing and ECG results from Visit 9 will be used to evaluate eligibility.
  15. If a subject is eligible and agrees to participate in the open label extension, the OLE study drug (40 mg or 80 mg) will be dispensed at V10. The subject should be instructed to take the first dose in the morning of the next day.
  16. Liver Safety Monitoring (laboratory analyte testing) must be performed at each study visit within the prespecified visit window OR the study drug dosing must be interrupted until the testing is done.
- Abbreviations: AD = Alzheimer's Disease; ADAS-Cog 11 = Alzheimer's Disease Assessment Scale-Cognitive Subscale 11; ADCS-ADL = Alzheimer's Disease Cooperative Study Group-Activities of Daily Living; AM = morning; ApoE = apolipoprotein E; BMI = body mass index; CDR-SB = Clinical Dementia Rating-Sum of Boxes; CSF = cerebrospinal fluid; CT = Computed Tomography; DNA = deoxyribonucleic acid; ECG = electrocardiogram; ET = Early Termination; FSH = Follicle Stimulating Hormone; HBsAg = Hepatitis B surface antigen; HCV-Ab = Hepatitis C virus antibodies; HIV 1 and 2 = Human Immunodeficiency Virus 1 and 2; MMSE = Mini-Mental State Examination; MRI = magnetic resonance imaging; NPI = Neuropsychiatric Inventory; PBMCs = peripheral blood mononuclear cells; *Pg* = *Porphyromonas gingivalis*; PK = pharmacokinetics; qPCR = quantitative polymerase chain reaction.

**Table 2. Schedule of Evaluations – Open Label Extension**

Study Period	Treatment Period 													Safety Follow-up		
	OLE-1	OLE-1a	OLE-2	OLE-2a	OLE-2b	OLE-3	OLE-3a	OLE-3b	OLE-3c	OLE-4	OLE-4a	OLE-5	OLE-6/ET	OLE-Phone Call		OLE-9
														OLE-7	OLE-8	
Visit number																
Week	50	52	54	56	58	60	63	66	69	72	78	84	96	97	98	102
Day	350 ± 3	364 ± 3	378 ± 3	392 ± 3	406 ± 3	420 ± 3	441 ± 3	462 ± 3	483 ± 3	504 ± 3	546 ± 6	588 ± 6	672 ± 8	679 ± 2	686 ± 2	714 ± 8
Evaluations																
Informed Consent																
Inclusion/Exclusion Criteria																
ADAS-Cog 11						X				X			X			X
ADCS-ADL						X				X			X			X
CDR-SB						X				X			X			X
Dispense Study Drug	X		X			X				X		X				
Concomitant Medications	X		X			X				X		X	X	X	X	X
Saliva Collection										X			X			X
Symptom-Based Physical Examination	X		X			X				X		X	X			X
Weight													X			
Vital Signs	X		X			X				X		X	X			X
Columbia-Suicide Severity Rating Scale	X		X			X				X		X	X	X	X	X
Liver Safety Monitoring 		X		X	X		X	X	X		X					
Safety Laboratory Tests	X		X			X				X		X	X			X
Urine pregnancy test 													X			
Adverse Events	X		X			X				X		X	X	X	X	X
12-Lead ECG	X		X							X			X			X
Oral Examination and collection of oral biomarker samples (only at selected sites) 													X			

 
1. A urine pregnancy test will be conducted only in women of childbearing potential. If the urine pregnancy test is positive, a serum pregnancy test will be performed to confirm pregnancy.
 
2. Oral biomarker samples include subgingival plaque and buccal cell swabs (only at selected sites). Visit OLE-6/ET oral examinations may be completed up to 8 days prior to OLE-6 Visit (or ET) when applicable.
 
3. Liver Safety Monitoring (laboratory analyte testing) must be performed at each study visit within the prespecified visit window OR the study drug dosing must be interrupted until the testing is done.
 
4. NOTE: Effective 16 February 2021, the OLE portion of the study was terminated by the Sponsor.
 
																

## List of Abbreviations

Abbreviation	Term
Abnormal CS	Abnormal Clinically Significant
Abnormal NCS	Abnormal Not Clinically Significant
AD	Alzheimer's disease
ADAS-Cog 11	Alzheimer's Disease Assessment Scale-Cognitive Subscale 11
ADCS-ADL	Alzheimer's Disease Cooperative Study Group-Activities of Daily Living
ADR	Adverse drug reaction
AE	Adverse event
AL	Attachment level
ANCOVA	Analysis of covariance
ApoE	Apolipoprotein E
B	buccal
Bid	Twice daily
BMI	Body mass index
BOP	Bleeding on Probing
CAL	Clinical Attachment Level
CDC/AAP	Centers for Disease Control/American Academy of Periodontology
CDR-SB	Clinical Dementia Rating-Sum of Boxes
CEJ	Cementoenamel junction
CFR	Code of Federal Regulations
CL	Creatinine clearance
CNS	Central Nervous System
CRA	Clinical Research Associate
CRO	Contract Research Organization
CS	Compound symmetry
CSF	Cerebrospinal fluid
CSH	Heterogeneous compound symmetry
C-SSRS	Columbia-Suicide Severity Rating Scale
CT	Computed Tomography
CV	Coefficient of variation
DB	Distobuccal
DL	Distolingual
DMC	Data Monitoring Committee
DNA	Deoxyribonucleic acid
ECG	Electrocardiogram
eCRF	Electronic Case Report Form

Abbreviation	Term
FDA	Food and Drug Administration
FSH	Follicle stimulating hormone
GM	Gingival margin
$\beta$ -HCG	Human chorionic gonadotropin
HbA 1c	Hemoglobin A 1c
HBsAg	Hepatitis B surface antigen
HCV-Ab	Hepatitis C virus antibodies
HIPAA	Health Insurance Portability and Accountability Act
HIV	Human Immunodeficiency Virus
HPMC	Hydroxypropyl methylcellulose
IB	Investigator's Brochure
ICF	Informed consent form
ICH	International Conference on Harmonisation
IEC	Independent Ethics Committee
IND	Investigational New Drug
INR	International Normalized Ratio
IRB	Institutional Review Board
IRS	Interactive Response System
ITT	Intent-to-Treat
L	Lingual
LP	Lumbar Puncture
MAR	Missing at random
MB	Mesiobuccal
MedDRA	Medical Dictionary for Regulatory Activities
ML	Mesiolingual
MMRM	Mixed-effects model for repeated measures
MMSE	Mini-Mental State Examination
MNAR	Missing not at random
MRI	Magnetic resonance imaging
NIA-AA	National Institute on Aging-Alzheimer's Association
NOAEL	No observed adverse effect level
NPI	Neuropsychiatric Inventory
PBMC	Peripheral blood mononuclear cell
PD	Pocket Depth
Pg	Porphyromonas gingivalis ( P. gingivalis [ Pg ])
PK	Pharmacokinetics
PP	Per Protocol
PT	Preferred Term

Abbreviation	Term
qPCR	Quantitative polymerase chain reaction
SAE	Serious Adverse Event
SAP	Statistical Analysis Plan
SD	Standard deviation
SGP	Subgingival plaque
$t_{1/2}$	Half-life
TEAE	Treatment-emergent adverse event
$T_{max}$	Time to maximum plasma concentration
ULN	Upper limit of normal

